4.2.2 PS Estimation

PS method will be used to balance the population-level baseline characteristics between the Trehalose treated group and the eligible historical control analysis set. In order to calculate PS, the following selected common baseline demographics and characteristics variables of known prognostic significance will be used as covariates in PS estimation if applicable, other covariates may also be included.

- Age (years) [19]
- BMI (kg/m^2)
- Bulbar onset (Yes/No)
- Riluzole use (Yes/No)
- Time since ALS symptom onset (months) [19]
- Time since ALS diagnosis (months)
- Baseline ALSFRS-R total score
- Pre-baseline ALSFRS-R slope (points/month) [20]
- Baseline % predicted VC [21]

PS is the probability of a participant being assigned to a treatment instead of the other one conditional on a given set of baseline characteristics. It is determined by a logistic regression with all above common baseline covariates. To reduce any potential bias due to rare events, PS will be estimated using penalized maximum

likelihood estimation (PMLE) (Firth, 1993). The PS will be estimated for participants from Trehalose group and the eligible historical control analysis set. Overlap of PS between both groups will be assessed using standardized mean differences table and/or plot.

4.2.3 PS Matching

PS matching method (Rosenbaum and Rubin, 1985) matches Trehalose participants with eligible historical control participants based on PS such that matched Trehalose participants and placebo participants are comparable in terms of covariates used in PS determination. This process mimics randomization to create two comparable groups with a caution of limitation that the matching is conditional on included covariates.

PS matching will be conducted in a 1:1 ratio using a more optimal caliper width based on the standard deviation of the logit of the propensity score [22]. The constructed historical control group will be used for the main analysis on the exploratory efficacy endpoints defined in Section 4.7. In addition, the propensity score matching will be performed with other different caliper widths if available to construct additional matched historical control groups for sensitivity analysis of the related exploratory efficacy endpoints.

Participants who are not selected in the matching process will be excluded from further analysis. Following matching, baseline covariates will be summarized for participants in PS matched Trehalose group and PS matched historical control group to check if the balance is generally achieved.

The PS matched identifier (ID) will be included as stratification factor to estimate the overall treatment effect and difference between the PS matched Trehalose group with historical control group in the analysis of exploratory efficacy endpoints defined in Section 4.7.

4.2.4 PS Stratification

The participants from Trehalose group and the eligible historical control analysis set will be sequentially stratified into appropriate strata according to the PS quintiles of the Trehalose treated participants. This allows each stratum to contain roughly an equal number of Trehalose treated participants. The strata that do not contain both Trehalose and historical control participants will be dropped from the matched samples. As participants in each stratum have similar propensity scores, each stratum can be conceptualized as a quasi-RCT, and the observed covariates will be better balanced between the two groups under the assumption that there are no unobserved confounders and the PS model has been correctly specified.

The overlap of PS distributions between the two groups within each stratum will be assessed. The covariate balance between the two groups after the PS stratification will be checked.

The PS stratification-built strata will be included as stratification factor to estimate the overall treatment effect and difference between the PS stratification-based Trehalose group and historical control group in the analysis of exploratory efficacy endpoints defined in Section 4.7.

4.3 Participant Disposition

A summary of participant disposition will be provided for Screened Set by treatment cohort and overall for the following categories. The number and percentage of participants will be presented.

- Participants screened (signed the informed consent form)
- Screen failures with reasons for failure

- Participants treated
- Participants with major protocol deviation
- Participants completed study or discontinued from study with discontinuation reasons
- Participants completed treatment or discontinued from treatment with discontinuation reasons

The study duration (weeks), defined as (date of study completion/discontinuation – date of informed consent signed + 1) / 7, will be summarized descriptively by treatment cohorts and overall.

The participant disposition for FAS and the participants who failed screening with reasons (if any) will be listed.

Protocol deviations for FAS will be provided in a listing including the deviation type and deviation description for major and minor deviations, respectively.

The number and percentage of participants included and excluded from the analysis sets FAS and PPS will be tabulated overall and for each treatment cohort. Reason(s) for exclusion from each set will be summarized overall and by reason for exclusion. The ALSFRS-R and SVC evaluable participants who have baseline and at least one post-baseline assessment of ALSFRS-R or SVC will be summarized under both FAS and PPS. The participants excluded from analysis sets and exclusion reasons will be listed for all Screened Set.

4.4 Participant Characteristics

The participant characteristics described in this section will generally be performed for FAS by treatment cohort and overall, unless otherwise specified. All related data will be provided in listings unless specified otherwise.

4.4.1 Demographic and Baseline Characteristics

Demographic data will be summarized descriptively including age (years) at time of first study treatment administration, age group (< 65 years, \geq 65 years), sex at birth, reproductive capacity, race, ethnicity and baseline physical measurements of height (cm), weight (kg), BMI (kg/m^2).

Baseline characteristics including ALS history, ALS diagnosis and ALS therapy as listed in items below will be summarized:

- Family history of ALS
- Site of onset (Limb, Bulbar, Axial, Respiratory, Generalized)
- Bulbar onset (Yes/No)
- Time since ALS symptom onset (months)
This equals to (date of first study treatment - date of ALS symptom onset + 1) / 30.4375
- Time since ALS diagnosis (months)
This equals to (date of first study treatment - date of ALS diagnosis + 1) / 30.4375
- Time since ALS symptom onset to diagnosis (months)
This equals to (date of ALS diagnosis – date of ASL symptom onset + 1) / 30.4375
- Has participant undergone genetic testing

- Has a genetic mutation been identified
- Type of identified mutation
- ALS Diagnosis made according to Revised El Escorial criteria
- Revised El Escorial Criteria for ALS
- Have genetically definite ALS
- Presence of tracheostomy (Yes/No)
- Presence of ventilation, noninvasive (NIV) (Yes/No)
- Gastrointestinal tube insertion (Yes/No)
- ALS medication use
 - None of Riluzole, Edaravone and Relyvrio
 - Any of Riluzole, Edaravone and Relyvrio (including subcategories: Riluzole, Edaravone, Relyvrio, Riluzole only, Edaravone only, Relyvrio only, Riluzole and Edaravone only, Edaravone and Relyvrio only, All of Riluzole, Edaravone and Relyvrio)
 - Neither Riluzole nor Edaravone, Both Riluzole and Edaravone

Participants' usage of these medications will be collected in concomitant medication form. These medications can be identified by the medication preferred term. Relyvrio is also called sodium phenylbutyrate/ursodoxicoltaurine, sodium phenylbutyrate/taurusodiol.

4.4.2 Baseline Assessments

Descriptive statistics will be used to summarize, by treatment cohort and overall, the following baseline assessments in the FAS.

- ALSFRS-R Total Score
- ALSFRS-R Severity Group: All ALSFRS-R Items ≥ 2 , One or More ALSFRS-R Items < 2
- Pre-baseline ALSFRS-R Slope (points/month)
This equals to $(48 - \text{baseline ALSFRS-R total score}) / \text{Time since ALS symptom onset (months)}$
- % Predicted SVC
- ALSAQ – Symptom Index
- ALSAQ - Physical Mobility
- ALSAQ - Activities of Daily Living/Independence
- ALSAQ - Eating and Drinking
- ALSAQ – Communication
- ALSAQ - Emotional Reactions

4.4.3 Baseline Characteristics Comparison with Historical Control

The common demographics and baseline characteristics outlined in Section 4.2.2 will be tabulated for PS matched (based on the pre-specified caliper width for main analysis) Trehalose group and historical control group under FAS and PPS, as well as PS stratification-based Trehalose group and historical control group under FAS and PPS.

The descriptive statistics for each baseline characteristics will be summarized; the standardized mean differences table and/or plot will be provided to assess the balance between two groups.

4.4.4 Medical History

Medical history will be classified using MedDRA terminology. Medical history will be summarized using numbers and percentages by primary system organ class and preferred term for each treatment cohort and overall for FAS.

4.4.5 Medications, Therapies and Procedures

4.4.5.1 Prior and Concomitant Medications

Prior medications are medications and therapies with a start date before the first dose of study treatment. Concomitant medications are medications with a start date after the first dose of study treatment. Medications with a start date before the first dose of study treatment and with either an end date after the first dose of study treatment or are ongoing will be classified as both prior and concomitant medications. If a medication or therapy cannot be classified due to completely missing dates, it will be classified as both prior and concomitant.

Prior and concomitant therapies/medications will be summarized by ATC drug class (i.e., 4th level, or most specific level available if 4th level is unavailable) and preferred name for each treatment cohort and overall based on the FAS.

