6.6.4 Prior and Concomitant Medication Review

It is important for the investigator or a designee to review each medication the participant is taking before starting the protocol and at each visit to monitor for potential interactions.

Concomitant medications (including any medication, vitamin, herbal preparation, or supplement) and procedures are those received on or after the first protocol treatment date (Day 0), including those started before Day 0 and continued after Day 0. At each visit, participant should be questioned about any new medication, vaccines, or non-drug therapies or changes to concomitant medications and nondrug therapies since the last visit. Concomitant medications and non-drug therapies, including the reason for use, start and end dates of administration, and dosage information should be recorded in the participant's medical chart.

Any concomitant medication deemed necessary for the participant's care during the protocol, or for the treatment of any AE, along with any other medications, other than those listed as disallowed medications may be given at the discretion of the investigator. However, it is the responsibility of the investigator to ensure that details regarding all medications are recorded in full in the participant's medical chart.

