4.4.5.2 Prior and Concomitant Devices/Procedures

The pre-specified key devices and procedures will be summarized by phase (Prior or Concomitant) and devices/procedure names for each treatment cohort and overall based on the FAS.

Prior devices/procedures are those with a start date before the first dose of study treatment. Concomitant devices/procedures are those with a start date after the first dose of study treatment. Devices/procedures with a start date before the first dose of study treatment and with either an end date after the first dose of study treatment or are ongoing will be classified as both prior and concomitant procedures. If a device/procedure cannot be classified due to completely missing dates, it will be classified as both prior and concomitant.

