Appendix 2 Date Imputation Rules

The following rule will be used for missing/partial date imputation.

Item	Missing or Partial Date Variable	Imputation Rule
Adverse events, prior/concomitant medications and procedures	Start date	
The day is missing but month and year are available
 
 • If the month and year of occurrence are the same as month and year of the first study treatment, the start date will be set to the date of the first study treatment. • Otherwise, if the month and year of occurrence are not equal to the month and year of first study treatment, the start date will be set to the first day of the month of occurrence. 
The day and month are missing but year is available
 
 • If the year of occurrence is the same as the year of the first study treatment, the start date will be set to the date of the first study treatment. • Otherwise, if the year of occurrence is not the same as the year of the first study treatment, the start date will be set to January 1 of the year of occurrence. 
The start date is completely missing
 
 • The start date will not be imputed. • Adverse events will be considered treatment emergent unless the end date suggests otherwise. • Medications/Procedures will be considered both prior and concomitant unless the end date suggests otherwise. 
EXCEPTION: If complete end date is available and the imputed start date is greater than the end date, then the assumed start date should be set to the end date.

	End date	
The day is missing but month and year are available
 
 • If the participant died and the partial stop date is in the same month and year as the date of death, the end date will be set to the date of death. • Otherwise, the end date will be set to the last day of the month of occurrence. 
The day and month are missing but year is available
 
 • If the participant died and the partial end date is in the same year as the date of death, the end date will be set to the date of death. • Otherwise, the end date will be set to December 31 of the year of occurrence. 
The end date is completely missing
 
 • The end date will not be imputed.

		EXCEPTION: If the imputed end date is less than the start date, then the end date should be set to the start date.

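### A medication or device/procedure whose start date equals the first-dose date has no prior or concomitant class under the SAP, and Appendix 2 moves two kinds of partial start date onto that day

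*SAP*

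**What the plan says.** SAP 4.4.5.1 sets two date rules for medications: "Prior medications are medications and therapies with a start date before the first dose of study treatment", and "Concomitant medications are medications with a start date after the first dose of study treatment". A third rule assigns both classes, but it too needs an earlier start: "Medications with a start date before the first dose of study treatment and with either an end date after the first dose", or ongoing. The only fallback is for missing dates: "If a medication or therapy cannot be classified due to completely missing dates, it will be classified as both prior and concomitant".

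SAP 4.4.5.2 repeats the structure: "Prior devices/procedures are those with a start date before the first dose of study treatment", and "Concomitant devices/procedures are those with a start date after the first dose of study treatment".

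SAP 4.1.3 says that dates imputed under Appendix 2 are used to decide prior or concomitant status. For a start date with the day missing in the month and year of first dose, or with day and month missing in the year of first dose, Appendix 2 says that "the start date will be set to the date of the first study treatment". If a complete end date falls before the imputed start, the start is moved to the end date instead.

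Protocol 6.6.4 uses a different boundary. Concomitant medications and procedures "are those received on or after the first protocol treatment date (Day 0"), including those begun earlier and continued. Day 0 in the protocol and Day 1 in the SAP are the same calendar day, the day of first dose.

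**The concern.** The two strict inequalities leave out one calendar day. It is not an arbitrary day: it is the day of first exposure, and the day that the SAP's imputation chooses for certain incomplete dates. A rule meant to make an incomplete record classifiable can therefore make it unclassifiable. A completely missing start date is counted as both prior and concomitant, unless the end date suggests otherwise, while a partly known date in the first-dose month can be counted as neither.

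The boundary also disagrees with the protocol, and with the treatment-emergent rule in SAP 4.9.2, which includes the first-dose date and uses the same Appendix 2 start-date rule. An adverse event dated only to the first-dose month is imputed to the first-dose date and counts as treatment-emergent. A medication recorded with the same partial date would have no class. At stake is the completeness of the medication and device/procedure summaries.

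**Working it through.** There is no sample size or power figure to reproduce. The check applies the written rules to every possible position of a start date.

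**Rules at date level.** Let F be the first-dose date, S the start date and E the end date.
- Prior: S < F.
- Concomitant: S > F.
- Both: S < F, and E > F or ongoing.
- Fallback to both: dates completely missing.

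If S = F, the first three conditions all fail, and the fallback does not apply because a date exists.

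**Scan of start dates.** For an ongoing medication, S was run from F − 400 to F + 400, which is 400 + 1 + 400 = 801 days. Exactly 1 of the 801 is unclassified: S = F.

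**Imputation cases.** F = 16 October 2023 is assumed for illustration only.

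| Recorded start | Recorded end | Start used | Class under SAP | Class if concomitant is S ≥ F |
|---|---|---|---|---|
| Full date, F − 1 | ongoing | F − 1 | both | both |
| Full date, F | ongoing | F | none | concomitant |
| Full date, F + 1 | ongoing | F + 1 | concomitant | concomitant |
| October 2023, day missing | ongoing | F | none | concomitant |
| October 2023, day missing | F + 10 | F | none | concomitant |
| October 2023, day missing | F | F | none | concomitant |
| October 2023, day missing | F − 5 | F − 5 (exception) | prior | prior |
| September 2023, day missing | ongoing | 1 September 2023 | both | both |
| November 2023, day missing | ongoing | 1 November 2023 | concomitant | concomitant |
| 2023 only | ongoing | F | none | concomitant |
| 2023 only | F − 60 | F − 60 (exception) | prior | prior |
| 2022 only | ongoing | 1 January 2022 | both | both |
| 2024 only | ongoing | 1 January 2024 | concomitant | concomitant |

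With the inclusive rule, 0 of the 801 start days are unclassified.

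**Other provisions that might close the gap.** The same-day convention in SAP 4.1.1 concerns assessments, under the definition of baseline, and does not reach medication start dates. SAP Section 7, which lists departures from the protocol, does not mention a narrower definition of concomitant.

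**The case against.** The best defence is that the intent is plainly inclusive. The protocol includes the day, the treatment-emergent rule includes it, records with completely missing dates go into both classes, and SAP Section 7 declares no change. A programmer who meets a record on the first-dose date has the protocol definition to apply. This stands as evidence that the wording is a drafting slip and not a deliberate departure. It does not repair the text, because the correction would have to be made without being written down.

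A second defence is that SAP 4.4.5.1 compares with the first dose, not with its date, so a drug given for a reaction to the first infusion did start after that dose. This is fair, and a reader should not infer that such a drug is certain to be missed. It is left unclassified only if the comparison is by date. That reading is likely, since protocol 6.6.4 asks for start and end dates of medications and not clock times, and an imputed date has no time. But the SAP does not state it.

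Third, a reader might infer that these records are excluded from the tables. No passage says so. SAP 4.4.5.1 does not specify separate prior and concomitant tables, although SAP 4.4.5.2 does split devices and procedures by phase. The table shells are in a separate Data Presentation Plan that is not among the documents. SAP 4.1 keeps collected data in listings, apart from data collected only for entry criteria or administration.

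**Conclusion.** The gap holds as a wording error with a limited effect. At date level, a start on the first-dose date has no class in SAP 4.4.5.1 or 4.4.5.2, contrary to protocol 6.6.4 and out of line with SAP 4.9.2.

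A reader might infer that partial start dates in general fall into the gap. They do not. Only the two cases in Appendix 2 reach the first-dose date. A complete end date before first dose takes a record out again, and other partial dates go to the first of the month or to 1 January and are classified.

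The number of records affected cannot be found from the documents. If the rule is followed literally, those records are missing from the descriptive FAS summaries of prior and concomitant medications and of devices and procedures. A wider effect is not supported: no efficacy or treatment-emergent analysis is described as using this status, and SAP 4.4.1 identifies ALS medication use by preferred term from the concomitant medication form.

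The conclusion assumes that the comparison is made on dates, and that the Data Presentation Plan does not already settle the point.

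**What to change.** In SAP 4.4.5.1 and 4.4.5.2, define concomitant by a start date on or after the date of first dose. Leave the prior definition and Appendix 2 as they are. Every start date then has a class, and the boundary matches protocol 6.6.4 and SAP 4.9.2. The cost is a few words in two paragraphs and the matching condition in the programs.

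A separate, optional clarification is how to treat a medication that started before first dose and ended on that date. The SAP already classes it as prior, so changing the end-date condition rescues no unclassified record. Protocol 6.6.4 can be read either way: receipt on the day favours adding the concomitant class, while its mention of treatment continued after Day 0 matches the present SAP.

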4.4.5.2 Prior and Concomitant Devices/Procedures

The pre-specified key devices and procedures will be summarized by phase (Prior or Concomitant) and devices/procedure names for each treatment cohort and overall based on the FAS.

Prior devices/procedures are those with a start date before the first dose of study treatment. Concomitant devices/procedures are those with a start date after the first dose of study treatment. Devices/procedures with a start date before the first dose of study treatment and with either an end date after the first dose of study treatment or are ongoing will be classified as both prior and concomitant procedures. If a device/procedure cannot be classified due to completely missing dates, it will be classified as both prior and concomitant.

4.5 Primary Endpoint Analyses

There is no statistical primary endpoint analysis based on the nature of this EAP study's primary objective is to provide access to the investigational product, SLS-005, to about seventy participants with ALS who are not eligible to participate in clinical trials.

4.6 Secondary Endpoint Analyses

Not applicable.

4.7 Exploratory Endpoints Analyses

This section includes the clinical efficacy analyses on overall survival, decline of ALSFRS-R, % predicted SVC and ALSAQ-40 scores. All endpoints will be summarized descriptively for EAP study treatment cohorts and overall. The first three efficacy endpoints (overall survival, ALSFRS-R, % predicted SVC) will also compare the treatment effect between combined Trehalose group with the historical control groups under both FAS and PPS as appropriate.

